9. STUDY MANAGEMENT	17
10. PUBLICATION POLICY	17
11. REFERENCES	18

GLOSSARY OF ABBREVIATIONS

CGM	Continuous glucose monitoring					
AI	Continuous glucose monitoring Adrenal insufficiency					
T1D	Type 1 diabetes					
ICRF	Type 1 diabetes Imperial College Research Facility					

KEYWORDS

Type 1 diabetes Adrenal Failure Hypoglycaemia Continuous glucose monitoring

STUDY SUMMARY

- **TITLE** Frequency of nocturnal hypoglycaemia in patients with insulin-treated diabetes and adrenal failure using prednisolone or hydrocortisone: a pilot study.
- **DESIGN** A prospective observational study
 - **AIMS** (1) To measure the frequency of nocturnal hypoglycaemic episodes in people with both AI and Type 1 Diabetes, and in age, sex and steroid replacement matched controls without diabetes.

(2) To compare frequency of nocturnal hypoglycaemia in those taking prednisolone versus those taking hydrocortisone.

[figure not shown]
(3) To compare the diurnal patterns of frequency of hypoglycaemia in those taking prednisolone versus those taking hydrocortisone.

- OUTCOME MEASURES Primary outcomes: Percentage time spent with glucose below 3.0mmol/L Secondary outcomes: Percentage time spent with glucose below 3.9mmol/L, between 3.9mmol/L and 10mmol/L, and above 10mmol/L. Number of episodes of hypoglycaemia and severe hypoglycaemia. Outcomes will be retrieved for the nocturnal period (midnight to 6am) and separately for the 24-hour period. Gold score, Hyperglycaemia Fear Survey-II (HFS-II) score and Hospital Anxiety and Depression (HADS) Score.
- POPULATION Adults with insulin-treated diabetes and adrenal insufficiency
 - **ELIGIBILITY** Confirmed diagnoses of insulin-treated diabetes and adrenal insufficiency for at least one year
 - **DURATION** 30 days

REFERENCE DIAGRAM

1. INTRODUCTION

BACKGROUND

Adrenal insufficiency (AI) is a serious condition which, without treatment, may be lifethreatening and is associated with increased mortality (1, 2). AI can be caused by primary failure of the adrenal glands (primary AI) or by pituitary disorders. Primary AI is an autoimmune condition that leads to destruction of the adrenal cortex and its ability to produce cortisol. Lack of cortisol can lead to an adrenal crisis which is an acute medical emergency requiring urgent treatment.

People with AI require lifelong steroid replacement, traditionally using hydrocortisone or more recently with prednisolone. Hydrocortisone has a short half-life and is given three times a day, which mimics the natural daily variation in production of cortisol. Prednisolone is an alternative option, and owing to its longer half-life needs only to be given once a day, offering benefits for ease of compliance.

Primary AI is often associated with other autoimmune endocrinopathies such as Type 1 diabetes, which requires treatment with insulin. Type 1 diabetes and type 2 diabetes, which may also require treatment with insulin, are both strongly associated with

cardiovascular risk factors (3) and increased mortality (4). Lifelong management with insulin requires multiple daily injections and self-management can be challenging.

Hypoglycaemia (low blood glucose) is a common and serious complication of insulin therapy and independently causes a twofold increase in risk for cardiovascular disease and mortality in insulin-treated diabetes (5). Hypoglycaemic symptoms may include irritability, dizziness or confusion. If left untreated this can lead to loss of consciousness, seizure or death. Prompt recognition and appropriate treatment is paramount and nocturnal hypoglycaemia is particularly concerning. Recurrent episodes may lead to impaired awareness of hypoglycaemia, increased frequency of episodes and subsequent risk of severe hypoglycaemia, defined as hypoglycaemia requiring the assistance of a third party for active treatment.

Hypoglycaemia also occurs in AI in the absence of insulin-treated diabetes. Cortisol has an important role in the counter-regulatory response to hypoglycaemia. Lack of cortisol in AI causes reduced hepatic glucose output and increased glucose oxidation leading to increased insulin sensitivity. Hypoglycaemia may be present in undiagnosed AI in some, and in others may be a signifier of untreated or suboptimal treatment of AI.

RATIONALE FOR CURRENT STUDY

There is a complex relationship between AI and Type 1 diabetes, which results in higher mortality in people living with both diagnoses compared to either diagnosis alone (6). Adrenal crises and hypoglycaemia are both potentially life-threatening medical emergencies which often lead to individuals requiring acute medical admission to hospital. Recent data demonstrates that more than half of severe hypoglycaemic episodes attended by paramedics result in conveyance to hospital (7). As having both conditions is rare, there are few studies on this high risk, vulnerable and relatively young group. There may be substantial potential to reduce harm and burden, and to reduce healthcare utilisation by minimising exposure to hypoglycaemia.

Previous studies conducted at ICHT reported 66% greater mortality in people with Al compared to matched controls (8). Furthermore, in people with primary Al, the mortality was three times higher in those with treated with prednisolone compared to hydrocortisone (9). These findings were reported from the first population-based dataset of adrenal failure in the UK. However, the studies were retrospective and prior to 2014, many participants took higher total daily doses of prednisolone (7.5g) than current recommended (3g or 4g). Research in optimal steroid replacement doses has since indicated that 7.5g is excessive, leading to steroid-induced complications such as hyperglycaemia, increased blood pressure and increased body weight, all of which increase cardiovascular risk factors. This is likely to have significantly contributed to the mortality excess in the past but further research in required to determine factors

affecting this group currently. This study would aim to investigate frequency of hypoglycaemia as a potential cause for this excess.

Research Question: In people with insulin-treated diabetes and adrenal failure, does hypoglycaemia occur more frequently in those treated with prednisolone or hydrocortisone?

2. STUDY OBJECTIVES

(1) To measure the frequency of nocturnal hypoglycaemic episodes in people with both AI and insulin-treated diabetes, and in age, sex and steroid replacement matched controls without diabetes.

(2) To compare frequency of nocturnal hypoglycaemia in those taking prednisone versus those taking hydrocortisone.

(3) To compare the diurnal patterns of frequency of hypoglycaemia in those taking prednisolone versus those taking hydrocortisone.

3. STUDY DESIGN

This is a prospective observational study in 16 adults with both insulin-treated diabetes and adrenal insufficiency and 16 age, sex and steroid replacement matched controls without diabetes. We will recruit and enrol 32 participants in total. Participants will spend 30 days in the study.

STUDY OUTCOME MEASURES

Primary outcomes: Percentage time spent with glucose below 3.0mmol/L

Secondary outcomes: Percentage time spent with glucose below 3.9mmol/L, between 3.9mmol/L and 10mmol/L, and above 10mmol/L. Number of episodes of hypoglycaemia and severe hypoglycaemia. Outcomes will be retrieved for the nocturnal period (midnight to 6am) and separately for the 24-hour period. Gold score, Hyperglycaemia Fear Survey-II (HFS-II) score and Hospital Anxiety and Depression (HADS) Score.

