7. STATISTICS AND DATA ANALYSIS

This is a pilot study and therefore we are not proposing a fully-powered study (4). The data gathered from the proposed work will serve as robust pilot data to support a larger randomised study.

The primary outcome is the percent time spent with glucose below 3.0mmol/L. This is in accordance with international consensus for hypoglycaemia. Glucose data will be extracted from the 30 days of unblinded/blinded CGM and used for analysis.

A two-tailed unpaired t-test will be performed to compare the primary and secondary glucose outcomes between groups. A p-value of <0.05 will be considered statistically significant.

All study data including personal and pseudoanonymised data and all appropriate documentation will be stored for a minimum of 5 years after the completion of the study, including the follow-up period.

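### Severe hypoglycaemia episodes, a sparse count over about 1.3 person-years, appear to be sent to an unpaired t-test that will often be undefined or uninformative; they need counts with exact intervals

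*Protocol*

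**What the plan says.** Protocol Section 3 (Study Outcome Measures) includes "Number of episodes of hypoglycaemia and severe hypoglycaemia" among the secondary outcomes, directly after the time-in-range percentages. It continues: "Outcomes will be retrieved for the nocturnal period (midnight to 6am) and separately for the 24-hour period". The questionnaire scores come after that sentence.

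Section 7 gives one method: "A two-tailed unpaired t-test will be performed to compare the primary and secondary glucose outcomes between groups". The decision rule is "A p-value of <0.05 will be considered statistically significant". No other method is named for episode counts.

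The only definition of a severe episode is in the background of Section 1: "severe hypoglycaemia, defined as hypoglycaemia requiring the assistance of a third party for active treatment". Section 3 fixes the size and length of the study: "This is a prospective observational study in 16 adults with both insulin-treated diabetes and adrenal insufficiency and 16 age, sex and steroid replacement matched controls", and "Participants will spend 30 days in the study". The protocol gives no severe-event rate, no expected count and no power figure. Section 7 says that the study is a pilot and not fully powered, and that its data are meant to support a larger randomised study.

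**The concern.** A t-test compares means and relies on a usable estimate of within-group variance. Severe episodes over 30 days will be zero for nearly every participant, so that variance is either zero or set by the one or two people who had an event. The prescribed analysis can then fail in two ways: it returns no result, or it returns a p-value that the data do not support.

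The stake is the use to which the pilot will be put. Someone planning the larger trial needs the number of episodes, the number of people affected, the person-time and the uncertainty around them. The t-test supplies none of these. If no event occurs, a blank or non-significant line could be read as evidence of little risk, when 16 people over a month cannot show that.

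**Working it through.** There is no figure in the protocol to reproduce on this point.

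**Inputs.** From Section 3: 16 insulin-treated participants, 16 controls, 30 days, and a night window of 6 of 24 hours. From Section 7: a two-sided unpaired t-test at 0.05. Assumed, because the protocol does not give them: an equal 8 v 8 split between prednisolone and hydrocortisone among the insulin-treated; severe-episode rates of 0.2 to 3 per person-year; Poisson counts; and episodes spread evenly over the day.

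**Exposure.** 16 × 30 / 365.25 = 1.31 person-years in the insulin-treated group, or 0.66 for 8 people.

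**Expected events and chance of none.** Expected = 1.314 × rate. P(none) = exp(−expected). The night figures use a quarter of the expected count.

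| Assumed rate per person-year | Expected, 24 h | P(none) | P(4 or more) | Expected, night | P(none), night |
|---|---|---|---|---|---|
| 0.2 | 0.26 | 77% | <0.1% | 0.07 | 94% |
| 0.5 | 0.66 | 52% | 0.5% | 0.16 | 85% |
| 1 | 1.31 | 27% | 4.5% | 0.33 | 72% |
| 1.5 | 1.97 | 14% | 14% | 0.49 | 61% |
| 3 | 3.94 | 2% | 56% | 0.99 | 37% |

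**No event.** Both means and both variances are zero, so t = 0/0 and is undefined.

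**One person affected.** t = 1.00 whether that person had one episode or four: p = 0.325 (16 v 16) or 0.334 (8 v 8).

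**Three people with one episode each v none.** p = 0.073 (16 v 16) or 0.060 (8 v 8), not significant.

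**Four people with one episode each v none, 16 v 16.**
- Mean 0.25; variance = (4 × 0.75² + 12 × 0.25²)/15 = 0.20; the other group's variance is 0.
- Standard error = √(0.20/16) = 0.112; t = 0.25/0.112 = 2.24 on 30 df; p = 0.033 (Welch 0.041).
- Fisher's exact test: 2 × C(16,4)/C(32,4) = 2 × 1820/35960 = 0.101.

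**The same pattern, 8 v 8.**
- Mean 0.5; variance = 8 × 0.25/7 = 0.286; standard error = √(0.286/8) = 0.189; t = 2.65 on 14 df; p = 0.019 (Welch 0.033).
- Fisher's exact test: 2 × C(8,4)/C(16,4) = 2 × 70/1820 = 0.077.
- The exact conditional Poisson test on four events v none gives 2 × 0.5⁴ = 0.125 for either group size.

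**How narrow that pattern is.** Four episodes in fewer people do not reach 0.05 by t-test: split 2+1+1, p = 0.094 (8 v 8: 0.082); 2+2, p = 0.154 (0.149); four in one person, p = 0.325 (0.334). With five people affected v none, both tests are significant: t-test 0.014 (0.004), Fisher 0.043 (0.026).

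**Behaviour under equal rates** (simulation, 200,000 runs per setting, rates 0.5 to 1.5 per person-year in both groups). The 8 v 8 t-test is undefined in 52% to 14% of runs and rejects in 0.03% to 0.7%. The 16 v 16 test rejects in 0.3% to 3.3%.

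**What an interval would say.** With 0 of 8 people affected, the exact two-sided 95% upper limit is 1 − 0.025^(1/8) = 37%.

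**The case against.** **The t-test may not apply.** Section 7 attaches it to glucose outcomes, just after describing the extraction of sensor data. An event defined by third-party help is not a sensor reading. If severe instead meant a sensor-detected episode, the t-test would clearly apply but the count need not be sparse. This stands in part. Coverage is the natural reading, since severe episodes are listed with the glucose measures and share their time windows, and no other method is given. It is still an inference. The ambiguity is itself a reason to add a sentence.

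**The event count is unknown.** A reader might infer that the study will yield zero to two severe events. The documents do not support that: they give no rate, and Section 1 calls the group high risk. At 3 per person-year about four events are expected, and the chance of zero to two is only 25%.

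**False significance is not the main hazard.** A reader might infer that the t-test will tend to declare spurious differences. Under equal sparse rates it rejects well below 5% of the time. Significance on four episodes needs four different people, all on one side, and nobody on the other. For insulin-treated people against controls without diabetes a real difference is expected, so a significant result there need not be false.

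**An undefined test does little harm in an unpowered pilot.** The report would simply state zero events, and no choice of test adds information that 1.31 person-years does not hold. True of the information. But the protocol keeps a significance rule for this outcome, and an exact interval shows how little a zero excludes.

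**Count methods are often left to an analysis plan.** That would answer a protocol that was silent. This one names a test, and a later document would have to depart from it.

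**Conclusion.** The point holds in a limited form. On the natural reading, the only test named is applied to a count it does not suit. The main failure is an undefined or uninformative result: a 77% to 2% chance of no event at all over 24 hours, and 94% to 37% at night, for assumed rates of 0.2 to 3 per person-year. The secondary failure is one specific pattern, in which the t-test crosses 0.05 (0.033 or 0.019) and Fisher's exact test does not (0.101 or 0.077).

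The exposure of 1.31 person-years and the p-values for each pattern are arithmetic. The expected counts rest on the assumed rates, the night figures also on an even spread over the day, and the 8 v 8 figures on an assumed split. The consequence is modest, because this is a secondary outcome of a pilot; the primary outcome is not touched.

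**What to change.** In Section 7, state that severe hypoglycaemia episodes are not analysed by t-test. For each group and each time window, report the number of episodes, the number of participants with at least one, and the person-time, with exact intervals: Clopper-Pearson for the proportion affected and exact Poisson for the rate. If any p-value is shown, take it from an exact test, such as Fisher's on participants affected.

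In Section 3, say whether a severe episode carries the third-party definition given in the background, and whether it counts as a glucose outcome.

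The cost is one or two sentences, with no change to sample size, visits or data collection. A question at Visit 1 about severe episodes in the previous 12 months would add person-time, but it is a new data item subject to recall error and is not needed for this correction.

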4. PARTICIPANT ENTRY

INCLUSION CRITERIA

- for test group:

Confirmed diagnoses of adrenal insufficiency and insulin-treated diabetes for more than one year.

Adults aged above 18 years

-for matched control group:

Diabetes mellitus excluded on baseline blood review Adults aged above 18 years

EXCLUSION CRITERIA

Measured eGFR ≤ 30 Acute illness Abnormal thyroid function Admission to hospital Pregnant or planning pregnancy Breastfeeding Enrolled in other clinical trials, except at the discretion of the chief investigator Have active malignancy or under investigation for malignancy Severe visual impairment Reduced manual dexterity Unable to participate due to other factors, as assessed by the Chief Investigators

WITHDRAWAL CRITERIA

The subject has a serious event related to study Investigator initiated discontinuation of study due to participation or equipment concerns Withdrawal of consent

<70% complete continuous glucose monitoring (CGM) data within 10 day run in period

Withdrawal will be immediate. Identifiable data already collected with consent will be retained and used in the study. No further data would be collected or any other research procedures carried out on or in relation to the participant.

5. ADVERSE EVENTS

5.1 Definitions

Investigational Medical Device

Medical device being assessed for safety or performance in a clinical investigation. This includes medical devices already on the market that are being evaluated for new intended uses, new populations, new materials or design changes.

Adverse Event (AE)

Any untoward medical occurrence, unintended disease or injury, or any untoward clinical signs (including an abnormal laboratory finding) in participants, users or other persons concerned with the medical device. These may, or may not be, considered related to the investigational device, device related procedure or comparator. If the AE is considered to have a reasonable causal relationship with the device, then it is considered to be an ADE.

Adverse Device Effect (ADE) An Adverse Event (AE) related to the use of an investigational medical device. This includes any AE resulting from insufficiencies or inadequacies in the instructions for use, the deployment, implantation or operation of the medical device or any malfunction. This also includes any AE that is a result of an error in use or intentional misuse of the medical device.

Device Deficiency Inadequacy of a medical device with respect to its identity, quality, durability, reliability, safety or performance. Device Deficiencies include malfunctions, misuse or use errors and inadequate labelling.

Serious Adverse Event (SAE) An Adverse Event that results in:

- Death.
- Life threatening illness or injury.
- Permanent impairment of a body structure or body function.
- Hospitalisation or prolongation of existing hospitalisation.
- Medical or surgical intervention to prevent life threatening illness, injury or impairment to a body structure or body function.
- Foetal distress, foetal death or congenital anomaly or birth defect.
- Is otherwise considered medically significant by the Investigator

This includes potential SAEs which were avoided as result of action or intervention. A planned hospitalisation for a pre-existing condition, or a procedure required in the protocol, without a serious deterioration in health, is not considered an SAE.

NOTE Device deficiencies that might have led to a serious adverse event where a suitable action had not been taken or an intervention had not been made or if circumstances had been less fortunate are handled under the serious adverse event reporting system.

Such adverse events should be reported as soon as possible. When reporting these events please include the total number of patients treated in the UK at the time of reporting.

Medical judgement should be exercised in deciding whether an adverse event is serious in other situations. Important adverse events that are not immediately lifethreatening or do not result in death or hospitalisation but may jeopardise the subject or may require intervention to prevent one of the other outcomes listed in the definition above, should also be considered serious.

Severity: The term "severe" is often used to describe the intensity (severity) of a specific event. This is not the same as "serious", which is based on patient/event outcome or action criteria.

Suspected Serious Device Effect (SADE) An Adverse Device Effect (ADE) that results in:

- Death.
- Life threatening illness or injury
- Hospitalisation, or prolongation of existing hospitalisation.
- Persistent or significant disability or incapacity.
- Foetal distress, foetal death or congenital anomaly or birth defect.
- Is otherwise considered medically significant by the Investigator

Any hospitalisation planned prior to enrolment is not a SADE.

Unanticipated Serious Adverse Device Effect (USADE) Serious adverse device effect which by its nature, incidence, severity or outcome has not been identified in the current version of the risk analysis report.

Responsibilities There are a number of responsibilities when managing adverse events. Below is a list of responsibilities for both the Investigator and the Sponsor (the Research Governance and Integrity Team (RGIT) will act on behalf of the Sponsor).

The CI has overall responsibility for the conduct of the study. The Principal Investigator (PI) has responsibility for the research at a local site where the study involves specified procedures requiring site-specific assessment. There should be one PI for each research site. In the case of this single-site study, the CI and the PI are the same person.

Investigator's Responsibilities

- 1. CI to report all SAEs within agreed timelines to Sponsor
- 2. CI to report SAEs within agreed timelines to Sponsor, REC and relevant NHS Trust Research and Development Office (R&D)
- 3. Provide the Sponsor with details of all AEs identified in the protocol as critical to the evaluation of safety within the agreed timeframes specified in the protocol.
- 4. Review SAE reports from Investigators and perform an evaluation with respect to seriousness, causality and expectedness.
- 5. Supply the Sponsor, REC and relevant NHS Trust R&D with any supplementary information they request.

Sponsor's Responsibilities

- 1. In collaboration with the Device Manufacturer, perform ongoing safety evaluation of the trial device and report any findings that may affect the health of subjects to the Device Manufacturer.
- 2. Promptly notify all Investigators and REC(s) of any findings that may affect the health of subjects.
- 3. Keep detailed written reports of all AEs reported by PIs and performing an evaluation with respect to seriousness, causality and expectedness.
- 4. Report all relevant safety information and SAEs to the relevant REC within the relevant timelines
- 5. Submit the annual report to Sponsor and REC.

Note that for Imperial AHSC sponsored studies the above sponsor responsibilities are delegated to the CI.

PROCEDURES

Study Planning The device's User Guide written by the device manufacturer lists known side effects and adverse reactions contained within the manufacturer's product information. Rare/very rare events may or may not be included depending on individual study requirements.

During the Trial Each AE will be evaluated for seriousness, causality, and expectedness. The responsibility for this evaluation and reporting to the sponsor rests with the CI.

Causality Adverse reactions will be assessed for causality. The definitions below will be used.

Relationship	Description
Unrelated	There is no evidence of any causal relationship to the
	medical device
Unlikely	The relationship with the use of the investigational medical
	device seems not relevant and/or the event can be
	reasonably explained by another cause.
Possible	The relationship with the use of the device is weak but
	cannot be ruled out completely
Probable	The relationship with the investigational medical device
	seems relevant and/or the event cannot be reasonably be
	explained by another cause.
Causal	The serious event is associated with the investigational
Relationship	medical device beyond reasonable doubt.

Assessment of Expectedness

Expected: The reaction is consistent with the effects of the device listed in the manufacturer's User Guide

Unexpected: the reaction is not consistent with the effects of the device listed in the manufacturer's User Guide .

Reporting

Once the CI has evaluated the AE in terms of seriousness, causality and expectedness, the following guidelines will be followed.

AEs/ADEs AEs that will be reported and are not considered serious will be included in the patient notes and on the relevant case report forms (CRFs). The completed form will be filed along with the other CRFs for the study.

SAEs/SADEs If the AE is assessed as serious, the CI must be informed immediately and within 24 hours. The CI will record the event with assessment of seriousness, (along with causality, expectedness and severity) on a trial SAE form. The CI will ensure that follow-up information is provided when available. Where supporting documents are sent with this form, these will be pseudonymised. Where the information available is incomplete at that time, as much information as can be ascertained will be sent to ensure timely reporting, with additional information provided as soon as it is known. Additional information received for an event (follow-up or corrections to the original event data) will to be detailed on a new SAE form. The CI must ensure that SAEs are reported to RGIT within 24 hours via email to [contact].

USADEs Reports of USADEs should be submitted to the REC within 15 days of the CI becoming aware of the event.

Follow-up of adverse events All adverse events will be followed-up until resolution or death of the participant.

